3.3 Analysis Populations

The Enrolled set will include all gymnasts who have provided informed consent and have been included into the study data base.

The Full Analysis Set (FAS) will be defined as all gymnasts randomly assigned to either the intervention or control group and who have responded to:

STATISTICAL ANALYSIS PLAN for NCT05506579

- Publication I: The OSTRC-H2 questionnaire either at baseline (Oct 2022) or Nov 2022 + one or more of April, May and June 2023.
- Publication II: The ICIQ-UI-SF questionnaire at baseline and in June 2023.

The Per Protocol Analysis Set (PPS) will include all randomised gymnasts meeting the study eligibility criteria and with no major protocol deviations affecting the intervention efficacy (FAS + completed 65% or more of the intervention sessions per week).

4 Trial Population

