5.1 Outcome Definitions

All outcomes will be analyzed on the full analysis set. An additional analysis of the primary outcome (in both publications) and the secondary outcomes I) (publication I) and I)-III) (publication II) will be performed on the per protocol set.

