5.2.3 Sensitivity analyses

A sensitivity analysis of the prevalence of injuries (primary outcome in publication 1) will be performed with a mixed effect logistic regression model where only the June measurement is used as an outcome. The model will have a fixed effect for group (intervention vs control) and a random intercept for club to account for the clustering of gymnasts within clubs.

STATISTICAL ANALYSIS PLAN for NCT05506579

A sensitivity analysis of the bother of UI (primary outcome in publication 2) will be performed with a quantile (median) regression model with the June measurement as dependent variable and group (intervention vs control) and the baseline (Oct) measurement as independent variables.

6 Statistical Software

All statistical analyses will be done in Stata version 17 (StataCorp LLC, College Station, TX, USA).

7 References

Clarsen, B., et al., *The Oslo Sports Trauma Research Center questionnaire on health problems: a new approach to prospective monitoring of illness and injury in elite athletes*. British journal of sports medicine, 2014. 48(9): p. 754-760.

Clarsen, B., et al., *Improved reporting of overuse injuries and health problems in sport: an update of the Oslo Sport Trauma Research Center questionnaires*. British Journal of Sports Medicine, 2020. 54(7): p. 390-396.

Ferreira, S., et al., Reeducation of pelvic floor muscles in volleyball athletes. Revista da Associação Médica Brasileira, 2014. 60(5): p. 428-433

Olsen, O.-E., et al., Exercises to prevent lower limb injuries in youth sports: cluster randomised controlled trial. BMJ, 2005. 330(7489): p. 449.

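### Every planned between-group analysis of urinary incontinence in Publication II uses only gymnasts with both an October and a June ICIQ, and none tests whether dropout affects the result

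*SAP*

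**What the plan says.** Section 3.3 opens the definition with "The Full Analysis Set (FAS) will be defined as all gymnasts randomly assigned to either the intervention or control group and who have responded to" and completes it for this paper with "Publication II: The ICIQ-UI-SF questionnaire at baseline and in June 2023". Both questionnaires are required.

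Section 5.1 then states "All outcomes will be analyzed on the full analysis set". The only other efficacy population is the per-protocol set, described in 3.3 as "FAS + completed 65% or more of the intervention sessions per week". Section 5.1 adds that the primary outcome and outcomes "I)-III) (publication II) will be performed on the per protocol set".

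Section 2.5 gives one ICIQ-UI-SF at baseline (October 2022) and one at the end of the intervention (June 2023), with none between. In 5.2.2 the primary ANCOVA and the UI-prevalence model both regress the June value on group and the October value. The one sensitivity analysis for this paper, in 5.2.3, is a "quantile (median) regression model with the June measurement as dependent variable", with the same two independent variables.

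Section 4.1 promises a CONSORT diagram with counts and reasons for loss to follow-up, discontinuation and exclusion from the primary analysis.

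**The concern.** The set called full is a complete-case set by definition. UI is measured once after baseline, about eight months later, so a gymnast who leaves or stops answering before June has no outcome and is defined out. The restrictions to gymnasts with UI or stress UI (SUI), the training-load subgroups and the per-protocol analysis only narrow this set further. The median regression changes the model but not who is analysed.

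The arms have different reasons to stop responding: one has an exercise programme to keep up, and the other receives nothing. If those who stop differ in June from what their arm and October score predict, and differ unequally between arms, the estimate is biased and every planned check inherits the bias. Superiority is claimed at two-sided p < 0.05 (2.4.2), so a shift of a few tenths of a point could matter.

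The October requirement is a second, smaller loss. A gymnast who answered in June has an observed outcome, and October enters the models only as a covariate.

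**Working it through.** **1. The plan's own figures.** Inputs from 2.3: means 4.7 and 2.5 (difference 2.2), SD 2.1, two-sided 5%, 80% power, design effect 1 + (9 − 1) × 0.05 = 1.4.

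n per arm = 2 × (1.960 + 0.842)² × 2.1² / 2.2² = 14.3, rounded up to 15. The total is 30, and 30 × 1.4 = 42. Both stated figures are reproduced. They serve here only as a scale for the effect.

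**2. Who is analysed.**

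| Analysis | Set | Restores an excluded gymnast? |
|---|---|---|
| ANCOVA of June score (5.2.2) | FAS | No |
| UI prevalence (5.2.2) | FAS | No |
| UI and SUI restrictions (5.1.2) | Subsets of FAS | No |
| Training-load subgroups (1.2.3, 5.1.4) | Subsets of FAS | No |
| Per-protocol (3.3, 5.1) | Subset of FAS | No |
| Median regression (5.2.3) | FAS | No |

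The SAP contains no imputation, no analysis of all randomised gymnasts and no analysis that varies the missing-data assumption.

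**3. Shift from missing June scores.** Let f be the fraction missing June in an arm, and d the number of points by which their June mean exceeds what the model predicts for them. The arm's true mean is the completer-based mean plus f × d. The shift in the completer difference towards benefit is therefore

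f_I × d_I − f_C × d_C.

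All f and d below are assumptions, since the SAP gives none.

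| f_I | f_C | d_I | d_C | Shift towards benefit |
|---|---|---|---|---|
| 0.20 | 0.20 | 1 | 0 | 0.20 |
| 0.20 | 0.20 | 2 | 0 | 0.40 |
| 0.20 | 0.20 | 2 | 2 | 0 |
| 0.20 | 0.20 | 0 | 1 | −0.20 |
| 0.20 | 0.20 | 0 | 2 | −0.40 |

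Against the planned 2.2 points, 0.20 is 9% and 0.40 is 18%.

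**4. What such a shift does to the test.** Assume no true effect, 110 enrolled per arm (the Publication I target), 20% missing, SD 2.1 without baseline adjustment, and design effect 1.4. The effective n per arm is 110 × 0.8 / 1.4 = 62.9, and SE = 2.1 × √(2/62.9) = 0.375. A shift of 0.20 (0.53 SE) raises the two-sided rejection rate from 5% to about 8%; a shift of 0.40 (1.07 SE) raises it to about 19%.

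**5. Cost of discarding June responders without October.** With clustering, the variance is proportional to [1 + (m − 1) × ICC] / m. Take m = 9 and ICC = 0.05 from 2.3, and assume that 5% or 10% of June responders lack October, spread across clubs.

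- m = 9: 1.4 / 9 = 0.1556
- m = 8.55: 1.3775 / 8.55 = 0.1611; √(0.1611 / 0.1556) = 1.018
- m = 8.1: 1.355 / 8.1 = 0.1673; √(0.1673 / 0.1556) = 1.037

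Confidence intervals are about 1.8% to 3.7% wider. Ignoring clustering, 1/√(1 − q) would give 2.6% and 5.4%, which overstates the loss.

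**The case against.** The strongest reply is that the rule mostly writes down what the model needs. With one follow-up measurement, an ANCOVA of June on October can use only gymnasts with both values. If June missingness depends only on arm and October score, that fit is unbiased, and imputing June from those same two variables adds essentially nothing. This stands. The gap is that the assumption is neither stated nor tested.

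The CONSORT diagram will show losses with reasons, and may reveal that they are unequal. That also stands, but counts cannot show what the losses did to the estimate.

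A reader might infer that the completer result will overstate the benefit of pelvic floor training. The SAP does not support that. Controls also answer monthly questionnaires and may stop, and symptom-free intervention gymnasts could leave while bothered ones stay, which would understate benefit.

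A reader might also infer from the Publication I rule, "Publication I: The OSTRC-H2 questionnaire either at baseline (Oct 2022) or Nov 2022 + one or more of April, May and June 2023", that missing October ICIQ scores are expected. That rule concerns a different, monthly questionnaire whose model excludes baseline. It says nothing about the ICIQ.

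Finally, adherence has no meaning for controls, and training load comes from the October questionnaire (2.5), as does the adherence denominator (3.2.1). Any imputation model has to respect this, and imputation for gymnasts with neither score rests on little information.

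**Conclusion.** The concern holds in limited form. The SAP itself fixes a completer set, runs every Publication II between-group analysis inside it, and plans nothing that varies the missing-data assumption. The protocol, which is not at hand, does not alter that, because this document defines the set and lists the sensitivity analyses.

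The SAP does not contradict itself here, and the primary ANCOVA can stay. Neither the size nor the direction of bias can be established; the 0.2 to 0.4 points and the 8% to 19% rejection rates follow from assumed dropout and are not predictions. The October exclusion is the minor part: about 2% to 4% in interval width, if 5% to 10% of June responders lack an October score. The change should be made, as a check on robustness rather than as the correction of a demonstrated bias.

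**What to change.** - **Section 3.3.** Define the Publication II FAS as all randomised gymnasts with a June ICIQ-UI-SF. In the ANCOVA and the UI-prevalence model, fill a missing October value with the pooled baseline value and add a missing indicator. This leaves the group comparison sound provided October response is unrelated to allocation. Analyses restricted by baseline UI or SUI status, or by training load, keep only gymnasts with that variable.
- **Section 5.2.3.** Add a sensitivity analysis over all randomised gymnasts. Multiply impute the June ICIQ separately by arm, using club, October ICIQ and training load, with adherence in the intervention arm only. Then shift the imputed scores over a range in each arm, including different shifts by arm, and report the shift at which the conclusion changes. The range should be fixed before unblinded data are seen.
- **Section 4.1.** Report June ICIQ response by arm.

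The cost is revised wording and one added analysis in Stata 17, with no new data. The sensitivity result may be less favourable than the completer result.

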4.1 Screening Data, Eligibility and Recruitment

The total number of invited clubs (with their gymnasts) and reasons for not entering the RCT will be summarised and tabulated.

A CONSORT flow diagram will be used to summarise the number of rhythmic gymnastics clubs/gymnasts who were:

- assessed for eligibility at screening (all rhythmic gymnastics clubs in Norway)
- eligible at screening (all rhythmic gymnastics clubs in Norway having gymnasts ≥ 12 years of age training ≥ 3 days per week)
- ineligible at screening*
- eligible and randomised (including number of gymnasts per club)
- eligible but not randomised* (including number of gymnasts per club)
- received the randomised allocation (including number of gymnasts per club)
- did not receive the randomised allocation* (N/A)
- lost to follow-up*
- discontinued the intervention*
- randomised and included in the primary analysis
- randomised and excluded from the primary analysis*

*reasons will be provided.

4.2 Baseline Patient Characteristics

The gymnast demographics and baseline characteristics to be summarised include age in years, weight, height, BMI, age when they started RG, competition level, weekly training load in hours, history of previous injuries and menstrual history.

Gymnast demographics and baseline characteristics will be summarised by randomised group and overall using descriptive statistics for continuous variables, and number and percentages of gymnasts for categorical variables. There will be no statistical analysis of group differences at baseline. Any clinical important imbalance between the groups will be noted.

STATISTICAL ANALYSIS PLAN for NCT05506579

5 Analysis

5.1 Outcome Definitions

All outcomes will be analyzed on the full analysis set. An additional analysis of the primary outcome (in both publications) and the secondary outcomes I) (publication I) and I)-III) (publication II) will be performed on the per protocol set.

5.1.1 Primary Outcome Definition

Publication I: The primary outcome is the prevalence of overuse injuries in the lower back, knees and hip/groin during the intervention period. In the OSTRC-H2 a health problem is defined as: “any condition that you consider to be a reduction in your normal state of full health, irrespective of its consequences on your sports participation or performance, or whether you have sought medical attention. This may include, but is not limited to, injury, illness, pain or mental health conditions.” Furthermore, an overuse injury is defined as: “an injury caused by multiple accumulative bouts of energy transfer without a single, clearly identifiable event responsible for the injury.” (Clarsen, et.al, 2020; Clarsen, et.al 2014). The primary outcome is dichotomous.

Publication II: The primary outcome is the bother of UI before and after the intervention period. Degree of bother is defined with the ICIQ-UI-SF sum score (0-21 points). The primary outcome is continuous.

5.1.2 Secondary Outcomes Definitions

Publication I: The secondary outcomes are:

- I. The prevalence of substantial overuse injuries in the lower back, knees and hip/groin during the intervention period. A substantial overuse injury is defined as “an overuse injury leading to moderate or severe reductions in sports performance or participation, or time loss” in the OSTRC-H2 (Clarsen, et.al, 2020; Clarsen, et.al 2014). The secondary outcome is dichotomous.
- II. The primary outcome and the secondary outcome number I) including overuse injuries in the calf/ankle/foot in addition to lower back, knees and hip/groin. The same definitions as listed above apply. The secondary outcome is dichotomous.
- III. The self-experienced effect and progress of the exercise program related to overuse injuries in the knees, lower back and hip/groin. The secondary outcome is continuous (score of -5 to 5).

Publication II: The secondary outcomes are:

- I. The prevalence of UI before and after the intervention period. The prevalence is defined by question 6 in the ICIQ-UI-SF. The secondary outcome is dichotomous.
- II. The primary outcome and the secondary outcome number I) restricted to gymnasts having UI. The secondary outcome is continuous.
- III. The primary outcome and the secondary outcome number I) restricted to gymnasts having SUI. The secondary outcome is continuous.

STATISTICAL ANALYSIS PLAN for NCT05506579

IV. The self-experienced effect and progress of the exercise program related to UI.
The secondary outcome is continuous (score of -5 to 5).

5.1.3 Overview of Outcomes Publication I

Level	Outcome	Timeframe	Type
Primary	Prevalence overuse injuries in the lower back, knees and hip/groin	Baseline (Oct 2022) + monthly for eight months (Nov 2022 – June 2023)	Dichotomous
Secondary	Prevalence substantial overuse injuries in the lower back, knees and hip/groin	Baseline (Oct 2022) + monthly for eight months (Nov 2022 – June 2023)	Dichotomous
	Prevalence overuse injuries and substantial overuse injuries in the lower back, knees, hip/groin, calf, ankle and foot	Baseline (Oct 2022) + monthly for eight months (Nov 2022 – June 2023)	Dichotomous
	Self-experienced effect and progress	After intervention (June 2023)	Continuous
Sub-group analysis	Prevalence overuse injuries and substantial overuse injuries in the lower back, knees, hip/groin, calf, ankle and foot for gymnasts training less or more than 15 hours per week	Baseline (Oct 2022) + monthly for eight months (Nov 2022 – June 2023)	Dichotomous

STATISTICAL ANALYSIS PLAN for NCT05506579

5.1.4 Overview of Outcomes Publication II

Level	Outcome	Timeframe	Type
Primary	Bother of UI	Baseline (Oct 2022) + after intervention (June 2023)	Continuous
Secondary	Prevalence of UI	Baseline (Oct 2022) + after intervention (June 2023)	Dichotomous
	Bother and prevalence of UI restricted to gymnasts having UI	Baseline (Oct 2022) + after intervention (June 2023)	Continuous / Dichotomous
	Bother and prevalence of UI restricted to gymnasts having SUI	Baseline (Oct 2022) + after intervention (June 2023)	Continuous / Dichotomous
	Self-experienced effect and progress	After intervention (June 2023)	Continuous
Sub-group analysis	Bother and prevalence of UI for all gymnasts training less or more than 15 hours per week	Baseline (Oct 2022) + after intervention (June 2023)	Continuous/ Dichotomous
	Bother and prevalence of UI restricted to gymnasts having UI training less or more than 15 hours per week	Baseline (Oct 2022) + after intervention (June 2023)	Continuous/ Dichotomous
	Bother and prevalence of UI restricted to gymnasts having SUI training less or more than 15 hours per week	Baseline (Oct 2022) + after intervention (June 2023)	Continuous/ Dichotomous

STATISTICAL ANALYSIS PLAN for NCT05506579

5.2 Analysis Methods

5.2.1 Publication 1

The outcomes prevalence of overuse injuries (primary outcome) and prevalence of substantial overuse injuries (secondary outcome) will be analyzed with multilevel mixed effect logistic regression models. The models will be fitted with outcome data from all time points (Nov, Dec, ..., June) except the baseline (Oct). The models will have a fixed effect for group (intervention vs control) and two random intercepts: gymnast and club, with gymnast nested within club. Based on the fitted model, we will present the odds ratio (OR) for injury (with 95% confidence interval [CI]) for intervention vs control and the P-value for the null hypothesis of an OR = 1.

The observed prevalence of injuries (with 95% CI) for each time point (Oct, Nov, ..., June) for the primary outcome and the secondary outcome I) and II) will be presented in a figure.

Self-experienced effect and progress is measures on a -5 to 5 scale and only measured after end of the intervention (June) and only for the gymnasts in the intervention group. We will present the observed number and percentage of responses in each category (-5, -4, ..., 4, 5) and also the mean and standard deviation of the responses.

5.2.2 Publication 2

Bother of UI (primary outcome) at the end of the intervention (June) will be analyzed with linear regression, with the June measurement as the dependent variable and group (intervention vs control) and the baseline (Oct) measurement as independent variables (ANCOVA). The standard errors in the model will be adjusted for the clustering of gymnasts within clubs. We will present the mean and standard deviation of the baseline and end-of-intervention measurements for each group and the estimated between-group difference in changes from baseline to end-of-intervention with a 95% CI. We will also give the P-value for the null hypothesis of a zero between-group difference.

The prevalence of UI (secondary outcome) at the end of the intervention (June) will be analyzed with a mixed effect logistic regression model with the June measurement as dependent variable and group (intervention vs control) and the baseline (Oct) measurement as independent variables. The model will contain a random intercept for club to account for the clustering of gymnasts within clubs. We will present the observed prevalence of UI for each group for each of the two time points, the OR for UI (with 95% CI) for intervention vs control and the P-value for the null hypothesis of an OR = 1.

Self-experienced effect and progress will be analyzed as described in section 5.2.1.

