1.1 Background and rationale

Overuse injuries are common among competitive Norwegian rhythmic gymnasts with a mean weekly prevalence of 37% [95% CI: 36% to 39%] and incidence of 4.2 new overuse injuries [95% CI: 3.6 to 4.9] per gymnast per year (Gram, M., Clarsen, B., & Bø, K., 2021). The knees, lower back and hip/groin were the most common injury locations. It has been postulated that reduced physical capacity (e.g strength, flexibility, stability) in the knees, lower back and hip/groin can increase the risk of injuries in rhythmic gymnastics.

In addition, more than 30% of the Norwegian rhythmic gymnasts experience urinary incontinence (UI), and 70% reported that UI negatively affected sports performance (Gram, M., & Bø, K., 2020). Few of the rhythmic gymnasts had any knowledge about the pelvic floor.

Hence, this assessor blinded cluster randomized controlled trial aims to find out whether the implementation of exercises targeting reduced physical capacity and pelvic floor dysfunction can prevent/reduce the prevalence of overuse injuries and UI.

The results from this RCT will be presented in two separate publications: **Publication I** on overuse injuries and **Publication II** on UI.

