2.5 Timing of Outcome Assessments

Publication I:

- Primary outcome: To assess the prevalence of overuse injuries in the lower back, knees and hip/groin, the Oslo Sports Trauma Research Center Questionnaire on Health Problems (OSTRC-H2) was used. The gymnasts in both groups answered the OSTRC-H2 at baseline (October 2022) and one time each month (last Sunday during the month) throughout the intervention period (November 2022 - June 2023).
- Secondary outcome:
 - I. To assess the prevalence of substantial overuse injuries in the lower back, knees and hip/groin, the same assessment method and time frame as listed above for the primary outcome was used.
 - II. To assess the primary outcome and the secondary outcome number I) including overuse injuries in the calf/ankle/foot in addition to lower back, knees and hip/groin, the same assessment method and time frame as listed above for the primary outcome was used.
 - III. To assess self-experienced effect and progress of the exercise program related to overuse injuries in the knees, lower back and hip/groin, a global rating of change (GRC) 11-point numerical scale was used. The gymnasts in the intervention group answered the GRC one time when the intervention period had ended (June 2023).

Publication II:

- Primary outcome: To assess the bother of UI, The International Consultation on Incontinence Questionnaire - Urinary Incontinence Short Form (ICIQ-UI-SF) was used. The gymnasts in both groups answered the ICIQ-UI-SF one time at baseline (October 2022) and one time when the intervention period had ended (June 2023).
- Secondary outcome:
 - I. To assess the prevalence of UI, the same assessment method and time frame as listed above for the primary outcome was used.
 - II. To assess the primary outcome and the secondary outcome number I) restricted to gymnasts having UI, the same assessment method and time frame as listed above for the primary outcome was used.
 - III. To assess the primary outcome and the secondary outcome number I) restricted to gymnasts having SUI, the same assessment method and time frame as listed above for the primary outcome was used.
 - IV. To assess self-experienced effect and progress of the exercise program related to UI, a global rating of change (GRC) 11-point numerical scale was used. The gymnasts in the intervention group answered the GRC one time when the intervention period had ended (June 2023).

STATISTICAL ANALYSIS PLAN for NCT05506579

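### The Publication I primary model leaves out October injury status, which is collected in both arms: the test is valid, but precision is lost and chance baseline imbalance stays in the odds ratio

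*SAP*

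**What the plan says.** Section 2.5 of the SAP establishes that the baseline value exists in both arms: "The gymnasts in both groups answered the OSTRC-H2 at baseline (October 2022) and one time each month". Section 5.2.1 fits the Publication I models to the November to June answers only and describes them thus: "The models will have a fixed effect for group (intervention vs control) and two random intercepts: gymnast and club, with gymnast nested within club". Group is therefore the only fixed effect. The June-only sensitivity analysis in section 5.2.3 is built the same way: "The model will have a fixed effect for group (intervention vs control) and a random intercept for club". October injury answers enter Publication I in two places only: the descriptive prevalence figure, and the rule for membership of the full analysis set in section 3.3.

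Publication II differs. Its ANCOVA (5.2.2), its mixed logistic model for the prevalence of incontinence (5.2.2) and its median regression (5.2.3) all take "group (intervention vs control) and the baseline (Oct) measurement as independent variables".

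On baseline differences, section 4.2 says only: "Any clinical important imbalance between the groups will be noted". Randomisation (section 2.2) is stratified by club size and not by injury status.

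**The concern.** The October answer uses the same instrument as the outcome and is a natural predictor of later injury reports. Leaving it out does not bias the comparison, but it gives up precision that needs no new data.

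The number of clubs is small: about 24, from 220 gymnasts at 9 per club (the SAP does not state a number). The arms can therefore differ noticeably in October by chance. The plan would note such a difference and leave it in the odds ratio, and any adjustment chosen after seeing it would be post hoc. The gymnast random intercept does not solve this. It models correlation among a gymnast's repeated answers but is assumed independent of group, so a chance difference between arms passes into the group effect.

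The wider interval and the chance imbalance are one source of variance seen in two ways, not two separate harms.

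**Working it through.** **1. The plan's own figure (section 2.3).** Inputs: 40% vs 20%, 80% power, two-sided 5%. Per arm: (1.960 + 0.842)² × (0.4×0.6 + 0.2×0.8) / 0.2² = 78.5, so 79 per arm and 158 in total, as stated. 158 × 1.4 = 221.2, against 220 stated. The figure reproduces and does not depend on baseline adjustment.

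**2. Size of a chance October imbalance.** Inputs: 40% prevalence, 110 per arm, design effect 1.4.

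- SD of the difference = √(0.4 × 0.6 × 1.4 × 2/110) = 0.078, or 7.8 points.
- P(difference beyond ±10 points) = P(|Z| > 0.10/0.078) = 0.20.

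**3. How much October can explain.** This depends on how persistent injury status is within a gymnast, which the SAP does not give. Two simple bounds follow.

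*Constant correlation ρ between months (assumed).* October's R² with the 8-month mean is ρ² / ((1 + 7ρ)/8), and the standard error is multiplied by √(1 − R²):

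| ρ | R² | SE multiplier |
|---|---|---|
| 0.1 | 0.05 | 0.98 |
| 0.3 | 0.23 | 0.88 |
| 0.5 | 0.44 | 0.75 |

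For the June-only model R² is ρ² (0.01, 0.09, 0.25), so the gain there is smaller.

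*Purely episodic injuries, identical gymnasts.* Section 1.1 gives "mean weekly prevalence of 37% [95% CI: 36% to 39%] and incidence of 4.2 new overuse injuries" per gymnast per year.

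- Mean episode = 0.37/4.2 years = 4.6 weeks.
- Onset rate = 4.2/0.63 = 6.7 per year; recovery rate = 4.2/0.37 = 11.4 per year; sum 18.0.
- One-month correlation = exp(−18.0/12) = 0.22.
- October then explains only 0.7% of the variance of the 8-month mean.

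**4. Simulation of the SAP's model with and without October.** 24 clubs × 9 gymnasts, 8 months, club SD 0.4 on the logit scale, nested intercepts fitted by quadrature, Wald test, 800 trials per cell. The club and gymnast SDs are assumptions. Each pair reads without → with October; the SDs are under the null.

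| Case | SD of log OR | Cut | OR factor per 10-point imbalance | Null rejection if imbalance > 10 points | Power, 40% vs 30% |
|---|---|---|---|---|---|
| Gymnast SD 2.0 | 0.355 → 0.272 | 23% | 1.37 → 1.05 | 19% → 3% | 54% → 74% |
| Gymnast SD 1.5 | 0.292 → 0.242 | 17% | 1.27 → 1.07 | 18% → 6% | 57% → 73% |
| Gymnast SD 1.0 plus monthly correlation 0.22 | 0.274 → 0.240 | 12% | 1.22 → 1.08 | 16% → 7% | 57% → 68% |
| Episodic, identical gymnasts | 0.224 → 0.215 | 4% | 1.16 → 1.14 | 15% → 14% | 62% → 65% |

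- Null rejection over all trials was 6–8% without October and 5–8% with it (Monte Carlo error about 0.8 points). In the imbalanced trials the error is about 3 points.
- Power at the planned 40% vs 20% was at least 99% either way.
- The mean log OR was the same with and without October (for example −0.725 and −0.726), so the SDs can be compared directly.

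**5. Larger variances.** With 400 trials per cell under the null, gymnast SD 1.5 and club SD 0.5 gave an SD of the log OR of 0.321 → 0.262 (18% cut). Gymnast SD 2.5 and club SD 0.7 gave 0.512 → 0.335 (35% cut). The mean log OR was about 0.03 with and without October, so neither model shows material bias.

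**The case against.** A randomised comparison with group as the only fixed effect is a legitimate, prespecified analysis. It is valid, and at the planned effect it is amply powered. The large gains assume strong, lasting differences between gymnasts. The one case derived from the SAP's own prevalence and incidence gives a 4% cut, and even those figures are for overuse injuries overall rather than the three sites of the primary outcome. The rejection rates of 15–19% apply only to trials picked for their imbalance, and the power gains to an effect smaller than the one planned. The contrast with Publication II is also softer than it looks. Its full analysis set requires an October answer, whereas Publication I admits "The OSTRC-H2 questionnaire either at baseline (Oct 2022) or Nov 2022 + one or more of April, May and June 2023", so a plain October covariate would drop gymnasts who answered first in November.

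Most of this stands as a limit on size. Validity is not in question, the gain may be close to nil if injuries are mainly episodic, and the conditional rejection rates are another view of the same lost precision. The slight excess over 5% in overall null rejection occurs with and without October and comes from Wald tests with few clubs, a separate matter.

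Two points do not stand. The missing October answers are handled by a third category. And a different data structure does not explain the omission: section 5.2.2 already adjusts a clustered binary prevalence outcome for its October value, and the SAP gives no reason for doing otherwise in Publication I.

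**Conclusion.** The concern holds as a loss of precision and robustness, not as bias or an invalid test. Adding October would cut the SD of the log odds ratio by about 4% in the purely episodic case and by 12–23% in the main cases where gymnasts differ, with more if the variances are larger. There is about a 20% chance of an October imbalance above 10 points. In the unadjusted model, 10 points moves the odds ratio by a factor of 1.16 to 1.37. Adjustment brings this to 1.05–1.08 where gymnasts differ, but only to 1.14 in the episodic case.

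Almost no power is at stake at 40% vs 20%. The benefit is a narrower interval, a result that depends less on the October split, and more power if the true effect is smaller than planned. The size rests on assumed gymnast and club variances and on about 24 clubs, none of which the SAP states.

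**What to change.** Add October status of the same outcome, coded no / yes / not answered, as a prespecified fixed effect in three places: the primary model, the models for secondary outcomes I and II (section 5.2.1), and the June-only sensitivity model (section 5.2.3). The third category keeps every member of the full analysis set. November should not stand in for a missing October answer, because it is an outcome month.

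Make the change before outcomes are examined by group. Section 2.5 describes data collection to June 2023 in the past tense, so that point may have passed. If it has, keep the current model as primary and report the October-adjusted one as a labelled sensitivity analysis.

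The cost is one line in each of the two sections and no new data. The downsides are an extra category for missing answers, an odds ratio that is conditional on October status, and little gain if injuries prove mainly episodic.
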